5.5.2 Withdrawal from the Trial

Subjects may withdraw from the trial at any time without giving a reason. Withdrawal of consent will be considered withdrawal from the trial.

A subject must be withdrawn in the event of any of the following:

- Withdrawal of the subject's consent.
- Participation in any other therapeutic trial during the treatment duration of this trial; however, subjects will continue to be followed for survival.

If a subject has failed to attend scheduled trial assessments, the Investigator must determine and record the reasons and the circumstances as completely and accurately as possible.

In case of withdrawal from the trial, the assessments scheduled for the last visit (End-of-Treatment visit) should be performed (see Section 7.1.4), if possible, with focus on the most relevant assessments. In any case, the appropriate End-of-Treatment electronic case report form (eCRF) visit must be completed. In case of withdrawal, subjects will be asked to continue safety and survival follow-up, which includes the collection of data on survival and subsequent anticancer therapy. After completion of the Follow-up period or after the End-of-Treatment visit, whatever is applicable, the appropriate eCRF section for Trial Termination must be completed.

CONFIDENTIAL INFORMATION

If a subject is withdrawn prior to disease progression for any reason in the expansion part of the trial, the subject will not be replaced. For the dose escalation part, subjects with the following events during the DLT observation period will be considered non-completers and have to be replaced: 1) deviation in MSB0011359C administration of greater than -3 days or +1 day due to reasons other than DLT; or 2) other condition that DLT is not evaluable (eg, use of non-permitted medicines).

5.6 Premature Discontinuation of the Trial

The whole trial may be discontinued prematurely in the event of any of the following:

- New information leading to unfavorable risk-benefit judgment of the IMP(s), eg, due to:
 - o Evidence of inefficacy of the IMP(s),
 - Occurrence of significant previously unknown adverse reactions or unexpectedly high intensity or incidence of known adverse reactions, or
 - o Other unfavorable safety findings.

(Note: evidence of inefficacy may arise from this trial or from other trials; unfavorable safety findings may arise from clinical or nonclinical examinations, eg, toxicology.)

- Sponsor's decision that continuation of the trial is unjustifiable for medical or ethical reasons.
- Poor enrollment of subjects making completion of the trial within an acceptable time frame unlikely.
- Discontinuation of development of the Sponsor's IMP(s).
- Withdrawal of the IMP(s) from the market for safety reasons (applicable to trials with marketed products only).

After primary analyses are completed, subjects may be offered to enroll into a roll-over trial before planned end of the trial.

The Health Authorities and Independent Ethics Committee (IEC)/Institutional Review Boards (IRBs) will be informed about the discontinuation of the trial in accordance with applicable regulations.

The whole trial may be terminated or suspended upon request of the Health Authorities.

5.7 Definition of End of Trial

If the trial is not terminated for any reason given in Section 5.6, the end of the trial is defined as 1 year after the last subject receives the last dose of MSB0011359C.

CONFIDENTIAL INFORMATION

6 Investigational Medicinal Product and Other Drugs Used in the Trial

The term "Investigational Medicinal Product" refers to an active substance or a placebo being tested or used as a reference therapy in a clinical trial, including products that have a marketing authorization but are formulated, packaged, or administered differently from the authorized form, used for an unauthorized indication, or used to gain further information about the authorized form. The only IMP used in this trial is MSB0011359C.

There is no placebo or active control arm in this trial.

6.1 Description of Investigational Medicinal Product

80/167

1

6.2 Dosage and Administration

of Subjects will receive intravenous infusion MSB0011359C over 1 hour (-10 minutes/+20 minutes, ie, over 50 to 80 minutes) once every 2 weeks as detailed in the Schedules of Assessments (see Table 1 and Table 2). Modifications of the infusion rate due to infusion-related reactions are described in Section 6.5.4.1. In order to mitigate potential infusion-related reactions, premedication with an antihistamine and with paracetamol (acetaminophen) (eg, 25 to 50 mg diphenhydramine and 500 to 650 mg paracetamol [acetaminophen] intravenous or oral equivalent) approximately 30 to 60 minutes prior to each dose of MSB0011359C is mandatory for the first 2 infusions. Premedication is optional and at the discretion of the Investigator after the second infusion. If Grade 2 infusion reactions are seen during the first two infusions, then premedication should not be stopped. Steroids as premedication Special precautions for monitoring of subjects and management of are not permitted. infusion-related reactions/hypersensitivity including modifications of the infusion rate and stopping of trial drug are described in Section 6.5.4 and subsections.

The starting dose of MSB0011359C in the dose escalation part is 3 mg/kg (dose escalation according to 3+3 design up to 20 mg/kg is intended) and the treatment cycle will be 2 weeks (14 days). The first subject of each cohort will be observed for at least 5 days before the second subject can be treated. Within each cohort, 48 hours must pass before a new subject can initiate dosing.

During the dose escalation part and for the HCC cohort, the dose of MSB0011359C will be calculated based on the weight of the subject determined on the day prior to or the day of each drug administration. For subsequent administrations, the dose will only be changed in case of weight gain or loss of $\geq 10\%$.

A flat dose of 1200 mg MSB0011359C will be used for all subjects in the expansion cohort (except for the HCC cohort) after confirming the tolerability of MSB0011359C at 20 mg/kg. Subjects will receive MSB0011359C once every 2 weeks until confirmed progression, unacceptable toxicity, or any criterion for withdrawal from the trial or IMP occurs (see Section 5.5). Subjects who have experienced a CR, PR or SD should continue treatment through the end of 12 months at the discretion of the Investigator and in consultation with the Medical Monitor. If the Investigator believes that a subject may benefit from treatment beyond 12 months, it may be permissible after discussion with the Medical Monitor.

For subjects who achieve a CR, PR, or SD on MSB0011359C therapy and then subsequently develop disease progression after stopping therapy, but prior to the end of the trial, 1 re-initiation course of treatment at the same dose and schedule and treatment duration up to 12 months is allowed at the discretion of the Investigator and agreement of the trial Medical Monitor. Subjects re-initiating treatment should be assessed according to the Schedule of Assessments for the expansion part of the trial (see Table 2).

CONFIDENTIAL INFORMATION

6.3 Assignment to Treatment Groups

The Investigator or delegate will assign a unique subject identifier number to eligible subjects in chronological order at the time of informed consent signature. Subject identifiers will be comprised of digits representing the trial number, the site number, and the subject number, which is allocated sequentially. Enrollment in the dose escalation and expansion parts will utilize an interactive web response system.

6.4 Non-investigational Medicinal Products to be Used

In order to mitigate potential infusion-related reactions premedication with an antihistamine and with paracetamol (acetaminophen) (eg, 25 to 50 mg diphenhydramine and 500 to 650 mg paracetamol [acetaminophen] intravenous or oral equivalent) approximately 30 to 60 minutes prior to each dose of MSB0011359C is mandatory for the first 2 infusions. Premedication is optional and at the discretion of the Investigator after the second infusion. If Grade 2 infusion reactions are seen during the first two infusions, then premedication should not be stopped. This regimen may be modified based on local treatment standards and guidelines as appropriate. Steroids as premedication are not permitted.

As with all monoclonal antibody therapies, there is a risk of allergic reaction including anaphylactic shock. MSB0011359C should be administered in a setting that allows for immediate access to an intensive care unit or equivalent environment and administration of therapy for anaphylaxis, such as the ability to implement immediate resuscitation measures. Steroids (dexamethasone 10 mg), epinephrine (1:1,000 dilution), allergy medications (intravenous antihistamines), bronchodilators, or equivalents, and oxygen should be available for immediate access. Infusion of MSB0011359C will be stopped in case of Grade ≥ 2 infusion-related, allergic, or anaphylactic reactions. Following MSB0011359C infusions, during the first 2 doses in the escalation phase there will be a minimum 24-hour in-patient observation. Please see the guidelines for handling of infusion-related reaction in Section 6.5.4.1.

If an allergic reaction occurs, the subject must be treated according to the best available medical practice. Guidelines for management of infusion-related reactions and severe hypersensitivity reaction according to the NCI are found in Section 6.5.4.

Further precautions are provided in Section 6.5.4. For prophylaxis of flu-like symptoms, a nonsteroidal anti-inflammatory drug (NSAID), eg, ibuprofen 400 mg or comparable NSAID dose, may be administered 2 hours before and 8 hours after the start of each dose of MSB0011359C intravenous infusion.

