5.1.3.2 Dose Escalation

The dose escalation will use a standard 3+3 scheme with the following planned doses:

- 3 mg/kg
- 10 mg/kg
- 20 mg/kg

The DLT period is defined as 21 days after the start of therapy. The first subject of each cohort will be observed for at least 5 days before the second subject can be treated. Thereafter, within each cohort, 48 hours must pass before a new subject can initiate dosing. Once the 3 or 6 subjects have passed the 21-day DLT evaluation period, the SMC will review the safety and available PK data to decide upon further dose escalation. Pharmacokinetics data from the previous cohort will be required for SMC review (eg, when the SMC is reviewing safety data from the 10 mg/kg cohort, available PK data from the 3 mg/kg cohort); however, PK data from the cohort under review will not be required).

For each dose level, DLTs are assessed during the first 3 weeks (Figure 1). The criteria for moving from one dose level to another do not allow escalation to the next cohort in cases where more than 1 subject in a cohort experience a DLT. If 1 of 3 subjects in a cohort experiences a DLT, this cohort will be expanded to 6 subjects with the SMC meeting after the 6th subject completes the DLT evaluation period.

The MTD is defined as the highest dose where no more than 1 subject out of 6 subjects experiences a DLT. Thus, the MTD cohort should accrue a total of 6 subjects (Figure 2).

After completion of the DLT evaluation at 3 and 10 mg/kg in the dose escalation part, enrollment in the HCC expansion cohort will start at 3 and 10 mg/kg, respectively.

After determination of the MTD in the dose escalation part, an MSB0011359C dose for further investigation will be selected and enrollment in the expansion cohorts of subjects with GC, ESCC, and BTC will begin (Figure 1).

The DLT criteria will not apply to any of the expansion cohorts.

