5.1.3.3 Dose-Limiting Toxicity

A DLT is defined as any Grade \geq 3 AE, with the exceptions described hereafter, assessed as related to IMP by the Investigator and/or Sponsor (ie, Grade \geq 3 adverse drug reaction [ADR]; grading

CONFIDENTIAL INFORMATION

according to the National Cancer Institute (NCI) Common Terminology Criteria for Adverse Events Version 4.03 [CTCAE v4.03]) occurring in the DLT evaluation period (21 days after first administration of MSB0011359C) confirmed by the SMC to be relevant for the IMP treatment. The SMC recognizes that in the absence of prior human experience with MSB0011359C, a conservative approach will be adopted in ascribing the relevance of the treatment-related toxicity to IMP. Treatment-related SAEs will be ascribed as related to drug except where a clear relationship to the underlying disease or recognized comorbidities is evident.

A DLT is defined as the following:

Any Grade \geq 3 AE that is related to MSB0011359C, occurring during the DLT evaluation period (21 days after administration of MSB0011359C), **except** for those listed below. Also, elevated alanine aminotransferase (ALT) or aspartate aminotransferase (AST) 3 times the upper limit of normal (ULN) and a concomitant elevation of bilirubin 2 times the ULN attributable to study drug constitutes a DLT.

- Grade 3 infusion-related reactions resolving within 6 hours from the end of infusion and controlled with medical management.
- Transient (≤ 6 hours) Grade 3 flu-like symptoms or fever, which is controlled with medical management.
- Transient (≤ 24 hours) Grade 3 fatigue, local reactions, headache, nausea, emesis that resolves to Grade < 1.
- Any Grade ≥ 3 drug-related amylase or lipase abnormality that is not associated with symptoms or clinical manifestations of pancreatitis.
- Grade 3 Hgb decrease (< 8.0 g/dL) that resolves to at least 9 g/dL within 14 days or the changes in the associated RBC parameters resolve within 14 days without blood transfusion or erythroid growth factor use.
- Malignant skin lesion that is local and can be resected with negative resection margin.

Dose-limiting toxicities that require treatment discontinuation are described in Section 5.1.7.2.

Subjects who do not complete the DLT observation period for reasons other than a DLT will be replaced.

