6.5.4.2 Severe Hypersensitivity Reactions and Flu-like Symptoms

If a hypersensitivity reaction occurs, the subject must be treated according to the best available medical practice. A complete guideline for the emergency treatment of anaphylactic reactions according to the Working Group of the Resuscitation Council (United Kingdom) and can be found at https://www.resus.org.uk/pages/reaction.pdf. Subjects should be instructed to report any delayed reactions to the Investigator immediately.

CONFIDENTIAL INFORMATION

A. Symptoms

- Impaired airway
- Decreased oxygen saturation (< 92%)
- Confusion
- Lethargy
- Hypotension
- Pale/clammy skin
- Cyanosis.

B. Management

- 1. Epinephrine injection and intravenous dexamethasone.
- 2. Patient should be placed on cardiac, blood pressure, heart rate, and oxygen saturation monitor immediately.
- 3. Alert intensive care unit for possible transfer if required.

For prophylaxis of flu-like symptoms, an NSAID, eg, ibuprofen 400 mg or comparable NSAID dose, may be administered 2 hours before and 8 hours after the start of each dose of MSB0011359C IV infusion except for the DLT period (for subjects who experienced a flu-like syndrome in the DLT assessment period, prophylactic use of an NSAID at the next dose is allowed).

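### Protocol 6.4 permits NSAID prophylaxis around every dose, Protocol 6.5.4.2 excludes the DLT period, and nothing says which governs during dose-limiting toxicity assessment

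*Protocol*

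**What the plan says.** Two sections of the Protocol set out NSAID prophylaxis of flu-like symptoms, with the same example drug, dose and timing.

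- **Section 6.4** says that the NSAID "may be administered 2 hours before and 8 hours after the start of each dose of MSB0011359C intravenous infusion". That sentence carries no exception. The one before it is a general pointer: "Further precautions are provided in Section 6.5.4".
- **Section 6.5.4.2** repeats the regimen but ends the permission with "IV infusion except for the DLT period". In parentheses it adds a carve-out for subjects who had a flu-like syndrome during DLT assessment: for them "prophylactic use of an NSAID at the next dose is allowed".

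Section 5.1.3.2 fixes the window: "The DLT period is defined as 21 days after the start of therapy". Section 5.1.3.3 counts related Grade 3 or higher events in that window as DLTs, subject to confirmation by the Safety Monitoring Committee (SMC). One of its exemptions is "Transient (≤ 6 hours) Grade 3 flu-like symptoms or fever, which is controlled with medical management".

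**The concern.** The occurrence of DLTs is a primary endpoint of the escalation part (Section 8.3.1). It also drives the 3+3 decisions and the maximum tolerated dose (MTD), because the rules "do not allow escalation to the next cohort in cases where more than 1 subject in a cohort experience a DLT". By tying its exclusion to the DLT period, Section 6.5.4.2 treats prophylaxis in that window as a separate matter. A site that follows Section 6.4 as written can give the NSAID at the first dose and so break the rule in 6.5.4.2 without knowing it.

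An NSAID given in advance could prevent or shorten a flu-like or febrile event that would otherwise have counted. If that happened, the observed DLT count would be lower than under the stricter section, and a dose would clear 3+3 more easily.

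**Working it through.** The plan states no figure on this point, so the check is mainly a comparison of text.

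**1. Which doses fall in the window.** Dosing is every 2 weeks, on Days 1, 15, 29 and so on. The window is 21 days, so the Day 1 and Day 15 doses fall inside it and Day 29 does not.

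**2. Where the two sections disagree.**

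| Dose | Subject | Section 6.4 | Section 6.5.4.2 |
|---|---|---|---|
| Day 1 | all | permitted | excluded |
| Day 15 | no flu-like syndrome so far in the window | permitted | excluded |
| Day 15 | flu-like syndrome earlier in the window | permitted | permitted |
| Day 29 onward | all | permitted | permitted |

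The conflict covers the first two rows only.

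**3. Whether another section settles it.**

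- Section 6.5.1 sends the reader to both 6.4 and 6.5.4 for prophylactic drugs, without ranking them.
- Section 6.5.2 restricts transfusions and erythroid growth factors in the DLT window. It does not list NSAIDs.
- SAP Appendix 1 mirrors this: code PDEV44 covers transfusions and growth factors. NSAID use in the window has no code of its own, only the catch-all PDEV99.
- Sections 5.5.1 and 5.5.2 require replacement of subjects whose DLT status is not evaluable, for example after non-permitted medicines. Section 5.5.1 refers to 6.5.2 for these. Since NSAIDs are not listed there, the text does not settle whether a subject given one at the first dose stays evaluable.

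**4. Which events could be lost.** Only events that are related, SMC-confirmed, Grade 3 or higher, flu-like or febrile, and outside the exemption for controlled Grade 3 events of 6 hours or less.

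**5. Direction of the effect, for illustration only.** The documents give neither a DLT rate nor a flu-like event rate, so the rates below are assumptions. With DLT probability p per subject, a dose clears 3+3 with 0 of 3 DLTs, or with 1 of 3 followed by 0 of 3:

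P(clear) = (1 − p)³ + 3p(1 − p)² × (1 − p)³

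For p = 0.30: 0.343 + 0.441 × 0.343 = 0.494.

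| Assumed true p | No masking | Observed rate lower by 0.05 | Observed rate lower by 0.10 |
|---|---|---|---|
| 0.20 | 0.709 | 0.814 | 0.906 |
| 0.30 | 0.494 | 0.600 | 0.709 |
| 0.40 | 0.309 | 0.397 | 0.494 |

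The table shows only that masking, if it occurred, would favour escalation and a higher MTD. The reductions of 0.05 and 0.10 are not estimates for this trial.

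**The case against.** The best defence is that the two sections can be followed together. Section 6.4 is permissive and points to 6.5.4 immediately beforehand. Section 6.5.4.2 is the dedicated section on flu-like symptoms and supplies the missing qualifier. A site that withholds the NSAID in the window complies with both. This holds as far as it goes, but the pointer does not mention an NSAID limit, the sentence after it grants permission for each dose, and no precedence is stated. A site that gives the NSAID complies with one section and breaks the other.

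The defence is stronger on impact. A reader might infer that the DLT rate was biased downward, or that it differed between sites. The documents support neither:

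- The NSAID is optional, and nothing shows that it was given in the window.
- Escalation runs at up to 2 sites in Japan, DLTs are monitored centrally, and the SMC reviews all treated subjects.
- Section 6.5 has concomitant drugs recorded with dose, duration and indication, so prophylactic use should be visible.
- Paracetamol, itself an antipyretic, is mandatory with an antihistamine at the first 2 infusions, which are the two scheduled in the window. Only the added effect of an NSAID is in question.

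A reader might also take all 18 subjects to be affected at both doses. Eighteen is the ceiling if all three cohorts expand to 6, and the Day 15 carve-out removes some subject-doses.

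Finally, the SAP (Section 4) reports that the last participant started on 24 August 2017, and the DLT criteria do not apply to the expansion cohorts. Amending the text now would not change any DLT observation already made. That stands, and it limits the amendment to clarity and interpretation.

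**Conclusion.** The contradiction is real and lies in current text. Sections 6.4 and 6.5.4.2 conflict at Day 1 for every escalation subject (at most 18) and at Day 15 for those without a prior flu-like syndrome. The consequence is a possibility: NSAID use under 6.4 could mask some qualifying flu-like or fever events, and any such effect would run toward fewer observed DLTs. Its size cannot be determined from the documents and may be small, given the mandatory paracetamol and the narrow class of events that remain. It is confined to the escalation part. The conclusion rests on the wording of the two sections and on the 14-day schedule set against the 21-day window; it does not depend on the assumed rates in the illustration. This is a minor inconsistency that is worth correcting.

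**What to change.** Reconcile Sections 6.4 and 6.5.4.2 so that both state the same rule for the DLT period, including whether the carve-out at the next dose applies. State also whether NSAID use contrary to that rule makes a subject non-evaluable for DLT, and align Section 6.5.2 if it does. Which rule is clinically right is for the sponsor and investigators to decide; no view is taken here. The cost is one clause, plus a short line on evaluability.

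Because the escalation windows are past, the sponsor can also check the concomitant-medication records of the escalation subjects for prophylactic NSAID use in the first 21 days and report the result beside the DLT findings. That uses data already collected, for at most 18 subjects.

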6.5 Concomitant Medications and Therapies

All concomitant medications taken by the subject during the trial, from the date of signature of informed consent are to be recorded in the appropriate section of the eCRF, noting the name, dose,

C O N F I D E N T I A L I N F O R M A T I O N

duration and indication of each drug. Nondrug interventions (other than vitamins) and any changes to a concomitant medication or other intervention should also be recorded in the eCRF.

6.5.1 Permitted Medicines

Any medications (other than those excluded by the clinical trial protocol) that are considered necessary to protect subject welfare and will not interfere with the trial medication may be given at the Investigator's discretion.

Other drugs to be used for prophylaxis, treatment of anaphylactic reactions, infusion-related reactions, and severe hypersensitivity reactions/flu-like symptoms and irAEs are described in Sections 5.1.7.2, 6.4, and 6.5.4.

Palliative bone directed radiotherapy may be administered during the trial. The assessment of PD will be made according to RECIST 1.1 (Eisenhauer 2009) and not based on the necessity for palliative bone-directed radiotherapy.

